Patients whose treatment is interrupted or permanently discontinued due to an AE including abnormal laboratory value must be followed at least once a week for 4 weeks and subsequently at 4-week intervals until resolution or stabilization of the event, whichever comes first. Dose interruptions should be reported on the appropriate Dosage Administration case report form (CRF). The maximum time allowed for toxicity-related treatment interruption is 21 days (3 weeks) from the intended dosing day. If interruption is > 3 weeks, the patient must be discontinued from the study treatment. However, the patient will continue to be followed for toxicity.

7. Population

Metastatic NSCLC: Male or female patients aged ≥ 18 years with histologically or cytologically confirmed metastatic squamous or non-squamous NSCLC whose disease has progressed after a platinum-based chemotherapy and after a single-agent immunotherapy. Patients with *EGFR* or *ALK* genomic tumor aberrations should have disease progression on FDA-approved therapy for these aberrations prior to receiving nivolumab. The investigator or designee must ensure that the patient meets all the inclusion and none of the exclusion criteria before being offered enrollment in the study.

Metastatic Uveal Melanoma: Male or female patients aged ≥ 18 years with histologically or cytologically confirmed metastatic uveal melanoma that is immunotherapy naïve.

Study Duration:

After administration of ADV/HSV-tk + Valacyclovir followed by SBRT, nivolumab will be given every 4 weeks from day 17 until disease progression, unacceptable toxicity, or up to 12 months in patients without disease progression. Patients will be followed up for 6 months or until disease progression, whichever occurs first. Patients will be assessed for AEs up to and including 30 days after the last treatment dose.

Safety Criteria:

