- Histologically or cytologically confirmed stage IV metastatic squamous or non-squamous NSCLC that has progressed after a platinum-based chemotherapy and after a single-agent immunotherapy **OR** histologically or cytologically confirmed metastatic uveal melanoma that is immunotherapy naïve.
- Evaluable or measurable disease as per RECIST 1:1, a target lesion of suitable diameter (at least 5 mm) for SBRT, and a non-target lesion of at least 1 cm in diameter for abscopal effect evaluation.
- ≥ 4 weeks since any major surgery.
- A 2-week washout period post any prior systemic anticancer therapy, RT, and/or investigational therapy is required prior to trial entry. Subject should be adequately recovered from the acute toxicities of any prior therapy.
- Life expectancy ≥ 6 months.
- ECOG performance status of 0–1.
- Adequate bone marrow function:
 - ANC $\geq 1.5 \times 10^9/L$ (without granulocyte colony stimulating factor support within 2 weeks of laboratory test used to determine eligibility)
 - Platelets $\geq 100 \times 10^9/L$ (without transfusion within 2 weeks of laboratory test used to determine eligibility)
 - Hemoglobin $\geq 8 \text{ g/dL}$ (without blood transfusion)
 - WBC count $> 2,500/\mu L$ and $< 15,000/\mu L$
 - Lymphocyte count $\geq 500/\mu L$
- Adequate liver function:
 - Serum bilirubin $\leq 1.0 \times \text{ULN}$ (patients with known Gilbert's disease who have serum bilirubin level $\leq 3 \times \text{ULN}$ may be enrolled)

- Serum transaminases (AST or ALT) activity $\leq 2.5 \times$ ULN with normal alkaline phosphatase (patients with liver metastases $\leq 5 \times$ ULN) OR AST and ALT $\leq 1.5 \times$ ULN with an alkaline phosphatase $> 2.5 \times$ ULN
- INR or PT and aPTT $\leq 1.5 \times$ ULN (unless patient is receiving anticoagulant therapy as long as PT or aPTT is within therapeutic range of intended use of anticoagulants);
- Adequate renal function: serum creatinine $< 2 \times$ ULN.
- WOCBP must have a negative serum pregnancy test within 7 days prior to the administration of the first study treatment. Women must not be lactating.
- WOCBP and men must practice an effective method of birth control (See Section 12.5).
- Signed informed consent to participate in the study must be obtained from patients after they have been fully informed of the nature and potential risks of the study by the investigator (or his/her designee) with the aid of written information.
- Willing to provide biopsies as required by the study.

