8.2 Exclusion criteria:

- Prior treatment with gene therapy.
- Any immunotherapy within 2 weeks of study treatment start (NSCLC cohort only).
- Prior treatment with immunotherapy (uveal melanoma cohort only)
- Patients with *EGFR* or *ALK* genomic tumor aberrations that have not received any FDA-approved therapy for these aberrations (NSCLC cohort only).
- Oxygen-dependent chronic obstructive pulmonary disease (NSCLC cohort only).
- Patients requiring oral prednisone for emphysema management (NSCLC cohort only).
- History of liver disease, such as cirrhosis or active/chronic hepatitis B or C.
- History of or current alcohol misuse/abuse within the past 12 months.
- Known gallbladder or bile duct disease (i.e., infection or cholecystitis) or acute or chronic pancreatitis.
- Major surgery within 4 weeks prior to study enrollment.
- Uncontrolled brain or leptomeningeal metastases or brain or leptomeningeal metastases requiring continued glucocorticoid treatment. Patients who have been treated at least 4 weeks prior to enrollment and have a CT or MRI scan of the brain showing no evidence of disease progression within 4 weeks of enrollment are eligible.
- Congestive heart failure: New York Heart Association class III or IV heart failure or unstable angina.
- History of syncope or family history of idiopathic sudden death.
- Sustained or clinically significant cardiac arrhythmias including sustained ventricular tachycardia, ventricular fibrillation, clinically significant bradycardia, advanced heart block (Mobitz II or higher atrioventricular nodal block), prolonged heart rate-corrected QT interval (longer than 470 milliseconds), or history of acute myocardial infarction. (The QT interval is the time between the start of the Q wave and the end of the T wave in the cardiac electrical cycle)
- Concomitant disease(s) that could prolong QT such as autonomic neuropathy (caused by diabetes or Parkinson's disease), human immunodeficiency virus (HIV), cirrhosis, uncontrolled hypothyroidism, or cardiac failure.
- Presence of active or suspected acute or chronic uncontrolled infection or history of immunocompromise, including a positive HIV test result.

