Treatment with other systemic/local anticancer agents (chemotherapy, immunotherapy, RT, hormone therapy, targeted or biologic agents) other than the protocol treatment is not permitted until disease progression is documented per modified irRC. Concomitant therapies will be continuously monitored from the first day of treatment.

11. Visit schedule and assessments

Visit	Screening ^a	Baseline ^b	V1	V2	V3	V4	V5	V6	V7	V8	V9	V10*	EOT
Day	-28 to -1	-7 to -1	0±5	2±5	4±5	7±5	9±5	11±5	17±5	45±5	73±5	101*±5	
Informed Consent	X												
Inclusion/Exclusion	X												
Demographics	X												
Medical History	X												
Physical Exam ^c	X		X						X	X	X	X	X
Height	X												
Weight	X		X						X	X	X	X	X
ECOG PS	X		X						X	X	X	X	X
12-Lead ECG and MUGA Scan or Echocardiogram ^d	X												X
Concomitant Therapies			Continuous from the first day of treatment										
Hematology ^e	X		X						X	X	X	X	X
Clinical Chemistry ^e	X		X						X	X	X	X	X
PT/INR/aPTT ^e	X								X	X	X	X	X
Serum Pregnancy (β-hCG) ^f	X												
Brain MRI ^g	X												
Tumor Assessments (RECIST 1:1 and irRC) ^h	X												X
Biopsy ⁱ			X						X				
Correlative Studies Blood Collection ^j	X								X		X		
Adverse Events and Serious Adverse Events			From informed consent signing up to and including 30 days after the last treatment dose ^l										
ADV/HSV-tk Administration ^k			X										
Valacyclovir Administration ^k			X										
SBRT Administration ^k				X	X	X	X	X					
Nivolumab Administration ^k									X	X	X	X	

Abbreviations: aPTT = activated partial thromboplastin time; AE = adverse event; ADV/HSV-tk = adenovirus-mediated expression of herpes simplex virus thymidine kinase; ANC = absolute neutrophil count; β -hCG = beta-human chorionic gonadotropin; CBC = complete blood count; CT = computed tomography; ECG = electrocardiogram; ECOG PS = Eastern Cooperative Oncology Group performance status; EOT = end of treatment; INR = international normalized ratio; irRC = immune-related response criteria; MRI – magnetic resonance imaging; MUGA, multigated acquisition; PET = positron emission tomography; PT = prothrombin time; RECIST = Response Evaluation Criteria in Solid Tumors; SAE = serious adverse event; SBRT = stereotactic body radiation therapy; WBC = white blood cell. A window of \pm 5 days is allowed for study visits and assessments (except as otherwise specified).

^aWithin 28 days prior to ADV/HSV-tk administration on day 0.

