12.3 Modified irRC, derived from RECIST 1.1¹⁹¹

This new classification is based on recent clinical studies showing delays in tumor regression or stabilization with cancer immunotherapies. For the ENSIGN trial, the concepts of the irRC are combined with RECIST 1.1 to come up with the modified irRC, which uses unidimensional measurements. For modified irRC, only target and measurable lesions are taken into account. In contrast to RECIST 1.1, the modified irRC criteria (a) require confirmation of both progression and response by imaging at eight 8 weeks after initial imaging (evidence of cancer progression within the first 3 months on bone scan only should be interpreted with extreme caution due to risk of tumor flare) and (b) do not necessarily score the appearance of new lesions as PD if the sum of the diameters of target lesions (minimum of 10 mm per lesion, maximum of 5 target lesions, maximum of 2 per organ) and measurable new lesions does not increase by $\geq 20\%$. The same assessment method and technique should be used to characterize each identified and reported target lesion(s) at baseline, during the trial, and at EOT. All measurements should be recorded in metric notation. The modified irRC based on RECIST 1.1 are displayed below. Modified irRC are defined as follows:

- New measurable lesions: Incorporated into tumor burden.
- New non-measurable lesions: Do not define progression but preclude irCR.
- Overall irCR: Complete disappearance of all lesions (whether measurable or not) and no new lesions. All measurable lymph nodes also must have a reduction in short axis to 10 mm or less.
- Overall irPR: $\geq 30\%$ decrease in the sum of the longest diameters of target and new measurable lesions.
- Overall irSD: Neither sufficient shrinkage to qualify for irCR or irPR (compared to baseline) nor sufficient increase to qualify for irPD (compared to nadir), using the sum of the longest diameters of target and new measurable lesions.
- Overall irPD: $\geq 20\%$ increase in the sum of the longest diameters of target and new measurable lesions increases (compared to nadir), confirmed by a repeat, consecutive observation at least 6 weeks (normally it should be done at 8 weeks) from the date first documented.

Documentation of immune-related PD (based on modified irRC) does not mandate discontinuation of the study treatment even after irPD is confirmed with CT scan 6 weeks after the initial observation of irPD.

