Appendix D: Modified irRC, derived from RECIST 1.1

Overall responses derived from changes in index, non-index, and new lesions

Measurable Response	Non-Measurable Response		Overall Response Using Modified irRC
Index and New, Measurable Lesions (Tumor Burden)	Non-Index Lesions	New, Non-Measurable Lesions	
Decrease 100%	Absent	Absent	irCR*
Decrease 100%	Stable	Any	irPR*
Decrease 100%	Unequivocal progression	Any	irPR*
Decrease \geq 30%	Absent / Stable	Any	irPR*
Decrease \geq 30%	Unequivocal progression	Any	irPR*
Decrease < 30% to increase < 20%	Absent / Stable	Any	irSD
Decrease < 30% to increase < 20%	Unequivocal progression	Any	irSD
Increase \geq 20%	Any	Any	irPD

* Assuming that the response (irCR and irPR) and progression (irPD) are confirmed by a second, consecutive assessment at least 4 weeks apart (normally it should be done 6 weeks apart).

Key Milestones:

FPFV / First Dose:

LPLV / Last Subject completed:

Database Lock:

Final Report:

Sponsoring Department: HMHCC &HMHRI

Prepared by: _____

Date _____

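### For EGFR/ALK carriers with NSCLC, Section 7 expects progression on approved targeted therapy, but the 8.2 exclusion asks only whether they received it

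*Combined protocol and SAP*

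**What the plan says.** Section 7 (Population) states that NSCLC patients with EGFR or ALK aberrations "should have disease progression on FDA-approved therapy for these aberrations prior to receiving nivolumab". Section 1.1 gives the same rule in its background account of nivolumab. The next sentence of Section 7 sets the enrollment check: "The investigator or designee must ensure that the patient meets all the inclusion and none of the exclusion criteria before being offered enrollment". The opening of Section 8 repeats that both lists must be satisfied.

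On the lists themselves:

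- Section 8.1 requires NSCLC that "has progressed after a platinum-based chemotherapy and after a single-agent immunotherapy". It does not mention EGFR, ALK or targeted therapy.
- Section 8.2 excludes, in the NSCLC cohort, patients with EGFR or ALK "genomic tumor aberrations that have not received any FDA-approved therapy for these aberrations".
- Section 8.1 also requires "A 2-week washout period post any prior systemic anticancer therapy" before trial entry.

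Once the patient is enrolled, Section 10 says that anticancer treatment, with targeted agents named among the examples, "other than the protocol treatment is not permitted until disease progression is documented per modified irRC". Section 12.3 defines progression under those criteria as an increase of at least 20% from nadir, "confirmed by a repeat, consecutive observation at least 6 weeks (normally it should be done at 8 weeks) from the date first documented". The footnote to Appendix D gives a shorter interval, assuming that response and progression "are confirmed by a second, consecutive assessment at least 4 weeks apart".

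**The concern.** Receiving a drug is not the same as progressing on it. Section 7's other two NSCLC requirements, progression after platinum and after single-agent immunotherapy, were carried into 8.1 intact. The EGFR/ALK requirement reached the lists only as a test of receipt. Monitoring checks the same lists: under Section 17, accrual review covers compliance with the inclusion and exclusion criteria, and the Annual Report asks whether participants met entry criteria. A carrier enrolled against the intent of Section 7 would therefore not need to be flagged.

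What is at stake is patient protection and a clear definition of who is in the NSCLC cohort. A patient with an approved drug that has not failed could go without it while receiving a single-arm experimental regimen, although the sponsor's own population statement says such a patient should have progressed first.

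**Working it through.** **Step 1: apply each section to the possible carriers.** Every patient below is assumed to have progressed after platinum and after single-agent immunotherapy, and to meet the remaining criteria.

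| Carrier's targeted-therapy history | Meets Section 7? | Passes 8.1? | Passes 8.2? |
|---|---|---|---|
| Never received an approved drug | No | Yes | No |
| Received it and progressed on it | Yes | Yes | Yes |
| Received it, disease still controlled on it | No | Yes, after washout | Yes |
| Received it, stopped for a reason other than progression | No | Yes | Yes |
| Progressed on one approved drug, controlled on a second | Yes on a literal reading | Yes, after washout | Yes |

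The sections disagree in rows three and four. Row five shows that copying Section 7 literally into 8.2 would still admit a patient whose current approved drug has not failed.

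**Step 2: look for another item that would catch rows three and four.** The Safety Criteria in Section 7 let the treating physician exclude a patient whose history, examination or laboratory findings put safety at risk. The general item in 8.2 concerns severe or uncontrolled conditions. Neither addresses a targeted drug that has not failed.

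**Step 3: time without the drug, for a patient still taking it (row three).** Inputs are the 2-week washout (8.1), CT at screening and every 8 weeks thereafter (Section 7), and confirmation at a minimum of 4 weeks (Appendix D), a minimum of 6 weeks (12.3) or normally 8 weeks (12.3). I assume that the washout ends at day 0, that only scheduled scans are used, that the first scan shows progression, and that visit windows are ignored.

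- Scan clock starting about day 0: washout + first scan + confirmation = 2 + 8 + 4 = 14 weeks, 2 + 8 + 6 = 16 weeks, or 2 + 8 + 8 = 18 weeks.
- Scan clock starting at a screening scan on day −28: the next scan falls on day 28, which is 28 + 14 = 42 days, or 6 weeks, after stopping on day −14. Adding confirmation gives 6 + 4 = 10 to 6 + 8 = 14 weeks.

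These are durations on scheduled scans alone. They are not fixed minimums, because an unscheduled scan or withdrawal can shorten them. For a patient who had already stopped the drug (row four), the washout may add nothing.

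**Step 4: the plan's own figure.** Section 15.1 states 80.3% power for 16 patients, ORR 3% versus 25%, one-sided 0.05. By exact binomial, rejecting at 3 or more responses gives P(X ≥ 3 | 16, 0.03) = 0.0113 and P(X ≥ 3 | 16, 0.25) = 0.8029, so the figure reproduces. This point does not challenge it, and a wording change in 8.2 does not alter it.

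**The case against.** The strongest reply is that Section 7 is operative protocol text. It states the progression requirement directly, and the sentence after it does not say that the lists override it. An investigator who follows both sections would not enroll these patients. This stands in part: it makes the problem an inconsistency between two sections, and a reader who infers that 8.2 overrides Section 7 goes further than the text. But Section 7 says should, and it names the lists as the check before enrollment is offered, so the looser rule can be applied without breaching the lists.

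Second, a reader might infer that the protocol orders a working drug to be stopped and then withholds it without escape. The documents do not say that. The washout applies to prior therapy and directs nobody to stop a drug; it is a condition a patient still on treatment would have to meet. Section 12.4 lets a subject leave at any time without giving reasons, and Section 7 allows CT at the physician's discretion or when clinically indicated. The bar therefore binds only while the patient stays on protocol.

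Third, the situation is uncommon. The patient must carry an aberration, have progressed after both platinum and immunotherapy, have a targeted drug that has not failed, and choose this trial. That stands, and it limits the severity.

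**Conclusion.** The inconsistency is real. Section 7 sets progression as the standard, 8.2 tests only receipt, 8.1 is silent, and the lists are the enrollment check. A carrier whose targeted drug has not failed can pass them.

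The size of the group cannot be estimated from the documents. Section 1.1 gives ALK 3.6% and EGFR 14% in a randomized trial of nivolumab against docetaxel in non-squamous NSCLC. A reader might infer 16 × (0.036 + 0.14) = 2.8 affected patients. That sum counts all carriers (assuming no overlap), in an all-non-squamous population not described as having failed immunotherapy, and says nothing about how many have a drug that has not failed. No such share is given anywhere.

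A reader might also infer a loss of power or a biased ORR. If one of the 16 could not respond, power would be P(X ≥ 3 | 15, 0.25) = 76.4%, but nothing in the documents supports assuming that such a patient could not respond. No effect on ORR or power is claimed.

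Severity is minor to moderate. The conclusion rests on the wording of Sections 7, 8 and 10, and on no assumed frequency.

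**What to change.** Replace the EGFR/ALK bullet in 8.2 with: *NSCLC cohort only: patients with an EGFR or ALK aberration whose disease has not progressed on FDA-approved therapy for it, including the most recent such therapy received.* Match the wording in Section 7. The reference to the most recent therapy is needed to catch a carrier who progressed on one approved drug and is controlled on another. The new bullet also covers carriers who have never been treated, so the present one can go.

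Whether patients who could not tolerate the targeted drug should remain eligible is the sponsor's choice. Neither Section 7 nor Section 1.1 contains such an exception; if one is added, it should be stated identically in Sections 7 and 8.2.

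The cost is one line in each section, made through the written amendment procedure in Section 16. A small number of candidates may be screened out. Sample size, test and visit schedule are unchanged.
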